
 To demonstrate the safety profile of triptorelin embonate 22.5mg 6-month formulation administered subcutaneously 	
 Incidence of TEAEs (including local tolerability) throughout the study i.e. up to Day 337 Change from baseline in clinical safety laboratory parameters (blood chemistry and haematology) at Day 337 Change from baseline in physical examination at Day 169 and Day 337 Change from baseline in ECG at Day 337 Change from baseline in vital signs (blood pressure and heart rate) at each visit up to Day 337

AE=adverse event; ECG=electrocardiogram; PSA=prostate-specific antigen; TEAE=treatment emergent adverse event

Note: A list of laboratory parameters to be assessed during the study are presented in Appendix 10.2.

The primary estimand for the primary endpoint is described below. The treatment will be triptorelin 6-month formulation administered subcutaneously. The population will comprise

participants with locally advanced and/or metastatic prostate cancer previously treated and castrated with a GnRH analogue as specified in the inclusion and exclusion criteria (Sections 5.1 and 5.2), respectively, that have received two scheduled treatment intervention doses (i.e. Day 1 and Day 169) and have completed all visits for measurement of testosterone.

The variable for the primary estimand will be castration maintenance rate during the study, which is defined as percentage of participants castrated (testosterone <1.735 nmol/L (50 ng/dL)) at Day 29, Day 85, Day 141, Day 169, Day 253, Day 309 and Day 337, with two complete study intervention administrations. Secondary estimands include analyses without using the visit window and/or using the ITT population where missing data will be considered a non-responder maybe conducted. Further details of the estimand will be specified in the SAP.

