7.2 Participant Discontinuation/Withdrawal from the Study

- A participant may withdraw from the study at any time at his own request or may be withdrawn at any time at the discretion of the investigator for safety, behavioural or compliance reasons.
- At the time of discontinuing from the study, if possible, an early discontinuation visit should be conducted, as shown in the SoA. See SoA for data to be collected at the time of study discontinuation and for any further evaluations that need to be completed.
- The reason for discontinuation will be recorded in the eCRF.
- If the participant withdraws consent for disclosure of future information, the sponsor may retain and continue to use any data collected before such withdrawal of consent.
- If the participant requests to discontinue the study intervention, they will be asked to be followed for the study procedures.
- If the participant withdraws consent for any further contact, the investigator will explain in the medical records as to whether the withdrawal is only from further receipt of study intervention or also from study procedures. This information must be entered in the eCRF.
- If a participant withdraws from the study, he may request destruction of any samples taken and not tested, and the investigator must document this in the site study records.
- A participant will be withdrawn from the study if they have inadequate testosterone suppression (defined as >50 ng/dL detected at least 30 days after the first administration of study intervention and on two consecutive measurements at least 2 weeks apart, at either a scheduled or unscheduled study visit).

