5.1.1 Outputs Presentation

5.1.1.1 Presentation of Visits / Timepoints

For by-visit summaries, the nominal visit as collected in the Electronic Case Report Form (eCRF) will be used in general for analysis purpose unless stated otherwise. Analysis visit window described in Section 6.1 will be used for slotting actual testosterone and prostate-specific antigen (PSA) assessment dates into planned schedule. Unscheduled visits will not be displayed in summaries but will be listed.

Visits in the TFLs will be presented as follows and in the following order:

Period	Long Visit Name	Short Name	Protocol Time Interval
Screening	Day -28 to Day – 1 (Screening)	Scr	
Intervention Period	Day 1 (Baseline)	Bsl	
	Week 1 – Day 3	D3	Day 3 after first injection
	Week 1 – Day 7	D7	Day 7 after first injection
	Week 4 – Day 29	D29	±3 day
	Week 12 – Day 85	D85	±3 day
	Week 20 – Day 141	D141	±3 day
	Week 24 – Day 169	D169	±3 day
	Week 25 – Day 171	D171	Day 3 after last injection
	Week 25 – Day 175	D175	Day 7 after last injection
	Week 36 – Day 253	D253	±3 day
EoS/ED	Week 44 – Day 309	D309	±3 day
	Week 48 – Day 337	D337	±3 day

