5.7.2.2 Primary Analysis

Primary analysis of castration maintenance rate will be based on the primary estimand in the FAS. Percentage of participants maintaining castrate levels of serum testosterone during the study along with the corresponding 95% exact CI will be provided in the FAS.

By-subject listing will be produced for all enrolled subjects.

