5.7.2.3 Sensitivity Analysis

Sensitivity analysis for the primary estimand is intended to assess treatment effects when using different strategies. Details are listed in the following.

Estimand ID	Primary-S1	Primary-S2	Primary-S3
Estimand	Primary	Primary	Primary
Analysis Type	Sensitivity	Sensitivity	Sensitivity
Analysis Set	ITT	ITT	ITT
Variable/Endpoint	Castration maintenance rate	Castration maintenance rate	Castration maintenance rate
Intercurrent Event	Strategy		
ICE1	Subjects will be included in the analysis regardless early withdraw status (Treatment policy)	Subjects will be included in the analysis regardless early withdraw status (Treatment policy)	Subjects will be included in the analysis regardless early withdraw status (Treatment policy)

Associated Procedure / Instruction Reference	319480-SOP
Form Reference	080091-FOR v7.0

IPSEN GROUP

CONFIDENTIAL

D-FR-52014-245

SAP Final: Version 1.0: 30 January 2023

PAGE 19/43

Estimand ID	Primary-S1	Primary-S2	Primary-S3
ICE2	With analysis window being applied, subjects without 2 consecutive missing testosterone value will be included in the analysis and subjects with at least 2 consecutive missing testosterone values will be considered as non-responders (Composite policy)	Without analysis window being applied, subjects without 2 consecutive missing testosterone value will be included in the analysis and subjects with at least 2 consecutive missing testosterone values will be considered as non-responders (Composite policy)	Analysis window is not applicable. Subjects with only one missing testosterone will be included in the analysis and available testosterone values will be analyzed as observed. For subjects with at least 2 missing testosterone values and without evidence of inadequate testosterone suppression (testosterone measurement ≥ 50 ng/dL), only testosterone values prior to the first missing will be included in the analysis. For subjects with at least 2 missing testosterone values and with evidence of inadequate testosterone suppression (testosterone measurement ≥ 50 ng/dL), available testosterone values will be analyzed as observed (Composite policy)
ICE3	Subjects will be included in the analysis regardless early treatment discontinuation status (Treatment policy)	Subjects will be included in the analysis regardless early treatment discontinuation status (Treatment policy)	Subjects will be included in the analysis regardless early treatment discontinuation status (Treatment policy)

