6 DATA HANDLING

6.1 Visit window

The time window for visit/timepoints will be applied as below for the blood samples for testosterone. In case of multiple unscheduled and planned visits enclosing within the defined analysis time interval, the non-missing value in a visit closest to the target visit day will be used in the summary tables.

Study phase	Scheduled visit	Protocol Time Interval	Analysis Time Interval* (days)
Screening	Day -28 to Day -1		-28 to -1
Intervention Period			
	Day 1 (first injection)	<1	<=1
	Week 1 – Day 3	3	2 to 5
	Week 1 – Day 7	7	6 to 18
	Week 4 – Day 29	29	19 to 57
	Week 12 – Day 85	85	58 to 113
	Week 20 – Day 141	141	114 to 155
	Week 24 – Day 169 (second injection)	169 (D2)	156 to D2
	Week 25 – Day 171	171 (D2+2)	D2+1 to D2+4
	Week 25 – Day 175	175 (D2+6)	D2+5 to D2+45
	Week 36 – Day 253	253 (D2+84)	D2+46 to D2+112
	Week 44 – Day 309	309 (D2+140)	D2+113 to D2+154
End of Study/Early Discontinuation	Week 48 – Day 337	337 (D2+168)	≥D2+155

*Analysis visit window after screening are defined using the mid-point between each scheduled visit and reset with the second injection.

6.2 Unscheduled Visits, Retest, Withdrawal Visit,

All listings will include retest measurement and assessments from unscheduled visits. For by-visit summary, only planned visits in the protocol will be presented.

Assessments from unscheduled visit and retest measurements will be included for baseline value determination whenever applicable. These measurements will also be used to determine worst toxicity grade for laboratory data, or meeting PCSA criteria in vital signs or ECG.

If an assessment requires a retest (for example, safety laboratory, vital signs and ECG), the closest non-missing value to the scheduled visit will be used in the summary tables.

Participants who have withdrawn early from the study have their last assessment entered at the end of study / early discontinuation visit in the eCRF.

Associated Procedure / Instruction Reference	319480-SOP
Form Reference	080091-FOR v7.0

IPSEN GROUP

CONFIDENTIAL

D-FR-52014-245

SAP Final: Version 1.0: 30 January 2023

PAGE 26/43

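### Primary-S2 can score an early leaver as castrated at Day 337 on an early-discontinuation sample taken up to 83 days before Day 337

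*SAP*

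**What the plan says.** The primary endpoint needs testosterone below 50 ng/dL at seven visits: Days 29, 85, 141, 169, 253, 309 and 337. The primary analysis (SAP 5.7.2.1) leaves out men who withdraw, miss a sample or miss the second dose, unless they had a value of 50 ng/dL or more (an escape). SAP 5.7.2.3 adds three sensitivity analyses in the ITT set.

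- **S1 and S2.** At least two consecutive missing values make a man a non-responder. For the rest, "subjects without 2 consecutive missing testosterone value will be included in the analysis". S1 applies the analysis windows of SAP 6.1. S2 does not: "Without analysis window being applied, subjects without 2 consecutive missing testosterone value" are handled as in S1.
- **S3.** This is a Kaplan-Meier estimate, and it does say how a single gap is scored: "Subjects with only one missing testosterone will be included in the analysis and available testosterone values will be analyzed as observed".

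Three other places decide which visit a sample belongs to when no window is applied.

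- SAP 5.1.1.1: "the nominal visit as collected in the Electronic Case Report Form (eCRF) will be used in general for analysis purpose unless stated otherwise".
- SAP 6.2: men who withdraw early "have their last assessment entered at the end of study / early discontinuation visit in the eCRF". In the tables of SAP 5.1.1.1 and 6.1 and in the protocol's Schedule of Activities, that visit is Day 337.
- Protocol 7.2: "if possible, an early discontinuation visit should be conducted, as shown in the SoA". The schedule includes a testosterone sample at that visit.

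Protocol Section 3 mentions, as optional, an analysis "using the ITT population where missing data will be considered a non-responder maybe conducted". The SAP does not schedule it.

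**The concern.** The primary analysis drops incomplete men without an escape but keeps every observed escape. The ITT analyses are the planned check on that choice, so they should not credit a man with a value from a visit he did not reach.

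S2 can do so. The second injection is meant to cover Day 169 to Day 337. A man sampled shortly after Day 253 has been observed for about half of that interval, yet S2 would record him as castrated at its end. The late part of the interval is where loss of suppression from a 6-month depot has to be looked for.

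**Working it through.** **1. The plan's own figures.** Inputs from SAP 2.3: 97% expected, 90% to be exceeded, one-sided alpha 0.025, exact binomial, n = 130, 10% drop-out.
- The Clopper-Pearson lower limit is 90.2% at 124/130, so at least 124 responders are needed. Exact alpha is 0.0207 and power is 90.3%.
- 130/0.9 = 144.4, rounded up to 145. Both figures reproduce.
- For 145 men the lower limit is 90.3% at 138/145 and 89.4% at 137/145, so 138 responders are needed.

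**2. Which leavers are affected.** Take D2 (second injection) = Day 169, Day 253 attended, and an exit sample on day e.

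| Exit sample | S2 (nominal visit) | S1 (dated windows, SAP 6.1) |
|---|---|---|
| Before the Day 253 visit | Days 253 and 309 missing: fails | Days 309 and 337 missing: fails |
| Day 254 to 281 (up to D2+112) | Only Day 309 missing; sample filed as Day 337: stays in | Sample goes to Day 253; Days 309 and 337 missing: fails |
| Day 282 to 308 (D2+113 to D2+139) | As in the row above | Sample goes to Day 309; only Day 337 missing: stays in |
| After Day 309, before Day 337 | Nothing missing: stays in | At most Day 337 missing: stays in |

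The earliest exit sample that S2 accepts as Day 337 is Day 254, and 337 − 254 = 83 days. S1 never files a sample as Day 337 unless it is dated D2+155 (Day 324) or later.

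**3. Size.** Assumptions: all 145 men are in the ITT set, 97% maintenance applies to leavers as well as completers, every leaver gives an exit sample, there are no sporadic gaps, and men with an isolated gap are scored on their available values. The documents do not give exit times, so two patterns are used: drop-out equal over the seven visit intervals, or uniform over the 336 days.

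Share of leavers who exit after Day 253: 2/7, or 84/336 = 0.25. Share who exit after Day 309: 1/7, or 28/336 = 0.083.

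- Strict rule, any missing value without an escape fails: 0.97 × 0.90 = 87.3%.
- S2 as written: 0.97 × (0.90 + 0.10 × 2/7) = 90.1%, or 0.97 × (0.90 + 0.10 × 0.25) = 89.7%.
- S2 with misdated samples treated as missing: 0.97 × (0.90 + 0.10 × 1/7) = 88.7%, or 0.97 × (0.90 + 0.10 × 0.083) = 88.1%.

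In men of 145, S2 exceeds the strict rule by 145 × 0.0277 = 4.0, or 145 × 0.02425 = 3.5. The misdated sample accounts for 145 × 0.0139 = 2.0, or 145 × 0.0162 = 2.3 of these. The rest are men who leave after Day 309, who at most lack Day 337.

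**4. Effect on the 90% bound.** The chance of at least 138 responders of 145 is 0.13% under the strict rule and 2.03% (equal intervals) or 1.48% (uniform) under S2. Every strict responder is also an S2 responder, so the share of trials in which only S2 clears is the difference: 1.90% or 1.35%.

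**The case against.** - **The route to Day 337 is inferred.** No sentence says that S2 uses an early-discontinuation sample as the Day 337 value. It follows from reading SAP 5.7.2.3, 5.1.1.1 and 6.2 together, and the nominal-visit rule applies only in general. This stands as a qualification. But no other rule for S2 is given, so a programmer following the text would arrive here.
- **The effect is small and S2 has no pass mark.** SAP 5.7.1.1 calls the efficacy analysis descriptive, and the 90% rule in SAP 2.3 belongs to the study objective. This stands. S2 on either side of 90% is only a way to judge size. Protocol 7.2 asks for the exit visit only where possible, so assuming a sample from every leaver gives the largest effect.
- **The fix brings a window back into the analysis meant to have none.** It does so for one value only. It checks whether an exit sample belongs to Day 337 and leaves every attended visit nominal.
- **A reader might infer that S1 and S2 count men with isolated gaps as responders by rule.** The text says only that they are included. Scoring on available values is the natural reading, because the contrast is with men called non-responders, but it is not stated. That is a missing detail.
- **A reader might infer that the SAP dropped a required strict analysis.** The protocol words it as optional, so leaving it out is no departure. The rate is also close to FAS responders over the ITT count, and both are already tabulated (SAP 5.2 and 5.7.2.2). The match is not exact, because the FAS requires two doses and the ITT set requires Day 1 testosterone below 50 ng/dL. In addition, "By-subject listing will be produced for all enrolled subjects". Only a labelled row and its interval are absent.

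**Conclusion.** The point holds for S2. With windows off, the SAP's remaining rules file an exit sample as Day 337 whatever its date, and a man who leaves between Day 253 and Day 309 can be scored as maintained on a value up to 83 days early. The 83 days rest on nominal visit dates and D2 = Day 169. S1 does not have this error.

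The consequence is modest. At the plan's own 97% and 10%, S2 reads about 89.7% to 90.1%, against 87.3% for the strict rule. About 2 of the roughly 4 men involved are due to misdating, and the two analyses disagree on the 90% bound in about 1% to 2% of trials. Larger disagreement needs drop-out or sporadic-missing rates that the plan does not give. The documents do not support a claim that the sensitivity analyses as a whole fail to test the primary result: S1 and S2 both fail most early leavers and are stricter than the primary analysis on them. The change is worth making because it removes a wrong score at almost no cost, not because it is likely to alter the study's conclusion.

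**What to change.** 1. **Change S2 (SAP 5.7.2.3).** Accept an early-discontinuation sample as the Day 337 value only if its actual date is D2+155 or later, the Day 337 window in SAP 6.1. Otherwise treat Day 337 as missing. All other visits stay nominal.
2. **Optional addition.** Report in the ITT set, with an exact 95% CI, the rate that counts any of the seven values missing without an escape as non-response. Label it a lower bound.
3. **Clarification only.** State how an isolated gap is scored in S1 and S2, for example on the available values as S3 does for one missing value.

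Cost: SAP wording and, if item 2 is adopted, one table row. No new data are needed, because sample dates are already used for the windows. The downside is less favourable rates. The bound in item 2 also penalises samples missed at random, and with 15 incomplete men it cannot exceed 130/145 = 89.7%, so it is neither a best estimate nor a test the study is sized to pass.

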2.3 Sample Size Determination and Power

This single-arm study is designed to demonstrate that the percentage of participants remaining castrated (maintenance of castration defined as testosterone <1.735 nmol/L (50 ng/dL) at Day 29, Day 85, Day 141, Day 169, Day 253, Day 309 and Day 337) during the study is greater than 90%. Considering an observed castration maintenance in 97% of participants, 130 eligible participants are required to demonstrate the efficacy of the triptorelin 6-month formulation with approximately 90% power and a one-sided alpha of 0.025 using an exact binomial test. The objective will be achieved if the lower bound of the 95% confidence interval (CI) of the observed rate is greater than 90%.

Considering a drop-out rate of 10%, 145 participants will be included in the study.

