ICE4	Same as primary estimand		
Population-level summary			
	Same as primary estimand	Same as primary estimand	Probability of Castration maintenance at Day 337 based on Kaplan-Meier estimate

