5.7.3.4 Sensitivity Analysis

For castration maintenance (<20 ng/dL) rate during the study, the Kaplan-Meier estimate at Day 337 using the same strategies as Primary-S3 with castration maintenance criteria replacing with as <20 ng/dL will be provided.

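### Primary-S3 censors men with two or more missing testosterone samples according to whether they later fail, so both of its Kaplan-Meier estimates are biased, though only slightly at the planned level of loss

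*SAP*

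**What the plan says.** Primary-S3 is one of three sensitivity analyses of the primary endpoint in the ITT set (SAP 5.7.2.3). For missing samples (ICE2) it sets three rules:

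- One missing sample, any outcome: "Subjects with only one missing testosterone will be included in the analysis and available testosterone values will be analyzed as observed".
- Two or more missing, no value at or above 50 ng/dL: "only testosterone values prior to the first missing will be included in the analysis".
- Two or more missing, "with evidence of inadequate testosterone suppression (testosterone measurement ≥ 50 ng/dL), available testosterone values will be analyzed as observed".

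Nothing in the third rule requires the high value to come before the first gap. The summary measure is "Probability of Castration maintenance at Day 337 based on Kaplan-Meier estimate". For maintenance below 20 ng/dL during the study, SAP 5.7.3.4 plans "the Kaplan-Meier estimate at Day 337 using the same strategies as Primary-S3", with the threshold replaced. The SAP gives no reason for treating the second and third groups differently.

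**The concern.** Take two men who both miss Day 29 and Day 85 and then attend every visit. One stays castrate throughout and is removed from the risk set before Day 29, so his five later castrate values are discarded. The other fails at Day 337; he stays at risk and his failure counts. The only difference between them is the later outcome. Kaplan-Meier estimation requires that censoring carry no information about the later event, and here it does by construction, even if the gaps are purely accidental.

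S1 and S2 count two consecutive missing values as non-response. S3 is the only sensitivity analysis of the primary endpoint that does not, and it is the only one planned for <20 ng/dL. If its own rule moves the estimate, a reader cannot tell how much of the result comes from missing data and how much from the rule.

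**Working it through.** **Inputs.** Seven scheduled efficacy samples, "at Day 29, Day 85, Day 141, Day 169, Day 253, Day 309 and Day 337" (SAP 2.3). Planning rate: "Considering an observed castration maintenance in 97% of participants, 130 eligible participants are required" (SAP 2.3). Loss of 10%, 145 enrolled, 90% criterion, one-sided alpha 0.025 (same section). The documents give no per-visit missingness, failure pattern or <20 ng/dL rate, so these are assumptions and are varied.

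**The plan's own figures.** No figure is stated for S3. The sample size reproduces: with n = 130 the smallest passing count is 124 (Clopper-Pearson lower bound 90.2%), giving exact alpha 0.0207 and power 0.903 at 97%. Also 130/(1 - 0.10) = 144.4, so 145.

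**The mechanism by hand (illustrative numbers).** Take 140 men with 4 failures, all at Day 337. Suppose 35 men miss Day 29 and Day 85 and then attend, and 1 of the 35 fails, the same rate as 3 of the other 105.

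- S3 as written: the 34 gap men who do not fail leave before Day 29. Estimate = 1 - 4/(140 - 34) = 1 - 4/106 = 96.2%.
- All 35 cut, whatever the outcome: 1 - 3/105 = 97.1%.
- None cut: 1 - 4/140 = 97.1%.

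The two even-handed rules agree. S3 is lower because the denominator loses the successes and the numerator keeps the failure.

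**How many men are affected.** With independent missingness m per visit, P(any gap) = 1 - (1-m)^7 and P(two or more) = 1 - (1-m)^7 - 7m(1-m)^6.

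- m = 1.5%: 1 - 0.8996 = 10.0% with any gap; 1 - 0.8996 - 0.0959 = 0.45% with two or more.
- m = 5%: 30% and 4.4%.
- m = 10%: 52% and 15%.

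The plan expects 130/145 = 89.7% evaluable, so 1.5% is the level consistent with it.

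**Simulation.** Seven visits, failure time uniform over visits, samples missing independently of outcome. Bias is in percentage points against the true rate.

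| True rate | Missing per visit | S3, sustained failures | S3, single-visit failures | All available values, single-visit failures |
|---|---|---|---|---|
| 97% | 1.5% | -0.01 | – | – |
| 97% | 5% | -0.10 | +0.04 | +0.13 |
| 97% | 10% | -0.37 | -0.09 | +0.25 |
| 80% (assumed, <20 ng/dL) | 1.5% | -0.05 | – | – |
| 80% (assumed, <20 ng/dL) | 5% | -0.56 | +0.31 | +0.86 |
| 80% (assumed, <20 ng/dL) | 10% | -2.07 | -0.30 | +1.68 |

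Using all available values for everyone is essentially unbiased for sustained failures but not for single-visit ones. Cutting every man at his first missing sample, whatever his outcome, stayed within 0.1 point of the truth in every scenario.

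**With 10% dropout added.** With sustained failures, S3 against all available values gives 96.85 against 96.96 (5% missing) and 96.50 against 96.90 (10%) at a true 97%. At a true 80% it gives 79.39 against 80.00 and 77.84 against 80.02. Dropout barely changes the gap: when no samples follow the first missing one, the rules coincide.

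**Comparison with the primary.** The FAS (SAP 4) excludes non-failures with any gap but keeps failures. At 97% with sustained failures its bias is about -1.2 points at 5% missing and -3.0 at 10%, against -0.10 and -0.37 for S3.

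**The case against.** The strongest case against is about size and consequence.

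- **Size.** At the missingness the plan implies, fewer than one man in 145 would have two or more gaps (0.0045 × 145 = 0.65), and the bias is a few hundredths of a point. Even that overstates it, because part of the planned loss is dropout, which is harmless here. The protocol also allows home visits except on injection days, which should limit intermittent gaps. This stands: the two-point figures need about half the men to have a gap, and a <20 ng/dL rate that no document supplies.
- **Consequence.** The efficacy analysis is declared descriptive, and the 90% criterion belongs to the primary rate. This also stands.
- **Remedy.** The obvious repair, analysing all available values for everyone, treats castration as having held through unmeasured gaps. Protocol 4.2 reports that in the earlier subcutaneous study some men were not maintained after the first injection, but all were after the second. Transient failures are therefore plausible, and with them that rule is biased upward by more than S3 at 5% and 10% missing. This stands and determines the fix below.

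None of this justifies the split by outcome.

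Three stronger readings are tempting but unsupported. A reader might infer that S3 cuts every non-failure at his first gap; one missing sample triggers no cut. A reader might infer that S3 is always conservative. The outcome-dependent censoring does pull it below the all-values estimate, but single-visit failures hidden in gaps push the other way, so the net error can have either sign. A reader might also infer that the rule drives S3 away from the primary. The primary FAS has the same asymmetry in stronger form, so the rule moves S3 slightly towards it.

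**Conclusion.** The rule is wrong as written, and the effect is small. In S3 and in the <20 ng/dL analysis that reuses it, censoring of men with two or more missing samples depends on the later outcome. With sustained failures both estimates are understated: negligibly at the planned loss, by about 0.1 point at 97% and 0.6 at an assumed 80% when 5% of samples are missing, and by about 0.4 and 2.1 when 10% are missing. These sizes rest on independent, random missingness and on assumed failure patterns and <20 ng/dL rates; the existence of the bias does not depend on the particular values chosen, provided that some men have two or more gaps and are sampled again afterwards.

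The practical harm is that S3 shares, in milder form, the selection it should help to test in the primary analysis. Neither the primary result nor the sample size changes.

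**What to change.** Replace the three ICE2 rules in Primary-S3 with one rule for every participant, and carry it into SAP 5.7.3.4: the event is the first value ≥50 ng/dL (≥20 ng/dL for the second analysis) observed before any missing scheduled sample; otherwise censor at the last sample before the first missing one, whatever is seen later.

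The cut should apply from the first gap, not only to men with two or more. The narrower version is also independent of outcome, but with single-visit failures it gave 80.66 for a true 80% at 5% missing with dropout.

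The all-available-values estimate can be shown alongside, with a note that it assumes castration held through unmeasured gaps and is biased upward if failures are transient. The composite label on this row should also go, since S3 does not count missing samples as failure.

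The cost is a SAP wording change and simpler programming, with no new data. The downside is that some observed later values, including some failures, are not used in the Kaplan-Meier estimate; a listing of post-gap failures would keep them visible.
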